- 4. Liver failure, cirrhosis, or any other liver disease that compromises liver function as determined by the investigator.
- 5. Hematocrit of less than 36% for men, less than 32% for women.
- 6. History of severe hypoglycemia during the past 12 months prior to screening visit or hypoglycemia unawareness as judged by the investigator. Participants will complete a hypoglycemia awareness questionnaire. Participants will be excluded for four or more R responses.
- 7. History of diabetes ketoacidosis during the prior 6 months prior to screening visit, as diagnosed on hospital admission or as judged by the investigator.
- 8. Adrenal insufficiency.
- 9. Any active infection.
- 10. Known or suspected abuse of alcohol, narcotics, or illicit drugs.
- 11. Seizure disorder.
- 12. Active foot ulceration.
- 13. Severe peripheral arterial disease characterized by ischemic rest pain or severe claudication.
- 14. Major surgical operation within 30 days prior to screening.
- 15. Use of an investigational drug within 30 days prior to screening.
- 16. Chronic usage of any immunosuppressive medication (such as cyclosporine, azathioprine, sirolimus, or tacrolimus).
- 17. Bleeding disorder, treatment with warfarin, or platelet count below 50,000.
- 18. Allergy to aspart insulin.
- 19. Current administration of oral or parenteral corticosteroids.

20. Any life threatening disease, including malignant neoplasms and medical history of malignant neoplasms within the past 5 years prior to screening (except basal and squamous cell skin cancer).

- 21. Beta blockers or non-dihydropyridine calcium channel blockers.
- 22. Current use of any medication intended to lower glucose other than insulin (ex. use of liraglutide).
- 23. Gastroparesis
- 24. Diets consisting of less than 50 grams of carbohydrates per day.
- 25. Any clinically significant disease or disorder which in the opinion of the Investigator may jeopardize the participant's safety or compliance with the protocol.

Subject Recruiting:

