Participants will receive training on how to use and calibrate the Dexcom G6 CGM system. The wire glucose sensor is sterile and commercially available from DexcomTM and will be used for single use only as directed by the manufacturer. Participants will be trained to insert the sensor into the subcutaneous tissue of the abdomen or flank after appropriate preparation of the abdominal skin as per the manufacturer's directions. Participants will be trained how to pair the Dexcom G6 transmitter to the Dexcom app on a provided study smart phone to start and stop a new sensor session and how to enter calibrations. The CGM alerts will be set at 70 mg/dL and 300 mg/dL. Participants will be given a Dexcom G6 transmitter and sensor to insert the day before each treatment visit along with a Contour Next meter for measuring their capillary blood glucose. The transmitter and sensors can be given to the participant at the CGM insertion visit or delivered via courier.

To reduce the risk of COVID-19 and to comply with OHSU modified operations, sensor insertion visits can be completed using Webex video conferencing software. Study devices, including a urine pregnancy test, will be delivered to participants via a courier. Using the Webex platform, study staff can connect virtually with participants for training on the devices and study procedures while they are at home.

1 day Treatment Visits

Participants will be asked to check glucose from CGM at 2am each morning before their treatment visit. If the CGM value is above 150 mg/dl, participants will be asked to enter this value into his/her pump calculator and take 80 percent of the correction bolus. The participant will be asked to check his/her glucose before driving to the clinic and to bring a snack in the car in case hypoglycemia does occur (in which case, the participant must park and treat the hypoglycemia). After the first treatment visit, the washout period will be 3 to 30 days calculated from the day of admission until the start of the next admission. After arrival at the OHSU OCTRI outpatient clinic, the Biomedical Engineering Point of Care (BME POC) Laboratory or Harold Schnitzer Diabetes Health Center clinic at approximately 7am, women of childbearing potential will receive a urine pregnancy test if the last pregnancy test was more than 7 days prior. This test must be negative before further participation is allowed.

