An assessment will take place at the beginning of the participant's first closed-loop study. We will inquire whether the participant has had changes in their medications and/or medical history to confirm the participant hasn't developed any study exclusion criteria. A capillary blood glucose (CBG) will be obtained and measured by a Contour Next glucose meter. When they arrive, participants will be given 15-20 grams of oral carbohydrate if the CBG reading is less than 70 mg/dl. CBG values > 300 mg/dl will be managed at the discretion of the investigator with a correction bolus and serum ketones will be checked. If serum ketones are ≥ 0.6 mM, the study will not be started and insulin therapy will be guided by the onsite investigator.

During each visit, glucose will be controlled using either: 1) the OHSU Robust R-AP closed-loop mode or 2) the OHSU MPC closed-loop mode. The order of the visits will be randomized. A code team is available by page at all times in all locations.

An Omnipod will be filled with Novolog or Humalog insulin for all studies. The Omnipod will be primed and inserted into the skin of the participant's abdomen or flank as directed by the manufacturer. Participants will disconnect his/her own pump and remove his/her own insulin infusion set once insulin delivery has started via the Omnipod. Participants will wear a Polar watch to inform the controller. The research staff will initialize the system and begin the closed-loop study. Two staff will review each of the settings to confirm the settings are inputted correctly. A member of the study staff will remain with the participant for the duration of the study with the study investigator on call. Research staff will set up and run the system and respond to all alerts.

The algorithm will push data up to a cloud server that can be monitored remotely every 5 minutes. The iPancreas will generate alerts on the smartphone according to Appendix D. In order to push alerts to study coordinators and study investigators, the cloud server used for remote monitoring will have a drop down menu for study staff to sign in and out for the duration of their monitoring shift. Each study coordinator and investigator listed in the menu will have a cell phone number on file that can receive texts with pushed alerts.

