Participant privacy will be protected by using a three-digit identifying number to code study documents. All paper source documents will be kept in a locked cabinet for a minimum of five years. All data from the study files on the smart phone master controller will subsequently be entered into the authorized electronic OCTRI Cloud database.

Recording of Data:

Investigators and staff will record data collected during the clinical trial on the CRF's. The CRFs will include:

- Screening form
- G6 Training Visit
- First Closed-loop Study Assessment
- First Closed-loop Study Visit
- Second Closed-loop Study Visit
- Adverse Event form
- Serious Adverse Event form
- Concomitant Medications

The Principal Investigators may authorize other personnel to make entries in the CRF.

The coded data collected during this study will be used for analysis of the primary and secondary endpoints listed in this protocol. The key to the code for this study will not be stored in the repository and only named study members on this project will have access to the key for this study. Researchers who request data from the repository will not receive any identifiers aside from date and we do not anticipate that the date will allow those researchers to re-identify the data. However, some of the researchers named on this project may use the data from the repository which would mean that the repository data will still be potentially identifiable to those who have access to the key as part of this project. The coded data will also be stored in the OregonAPC repository according to IRB protocol 19858. During screening, all new participants will sign the consent form to store their study data in the data repository. The data to be collected includes: (1) glucose sensor data, (2) blood glucose data, (3) insulin data, (4) physical activity data, and (5) food data. All data, except for blood glucose, is aggregated by the iPancreas app. The blood glucose data is collected through downloading the Contour Next BG meters and exporting data as an excel file. There are no biological specimens collected during this study.

Monitoring Procedures:

This protocol is written in accordance with the principles established by the 18th World Medical Assembly General Assembly (Helsinki, 1964) and amendments and clarifications adopted by the 29th (Tokyo, 1975), 35th (Venice, 1983), 41st (Hong Kong, 1989), 48th (Somerset West, South

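### The check for newly developed exclusion criteria is written for the first closed-loop study only, although the second crossover period may start up to 30 days later

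*Combined protocol and SAP*

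**What the plan says.** Under 1 day Treatment Visits, the protocol states: "An assessment will take place at the beginning of the participant's first closed-loop study". The next sentence gives content and purpose: "We will inquire whether the participant has had changes in their medications and/or medical history to confirm the participant hasn't developed any study exclusion criteria".

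The same section sets the interval between periods: "the washout period will be 3 to 30 days calculated from the day of admission until the start of the next admission".

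The list of forms under Recording of Data follows the same pattern. It includes "First Closed-loop Study Assessment", but for period 2 only "Second Closed-loop Study Visit". It also includes "Concomitant Medications", with no collection time and no link to whether a visit may start.

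Several Exclusion Criteria describe the participant's present state and so can begin between visits. Item 19 is an example: "Current administration of oral or parenteral corticosteroids". Items 9 (active infection), 21 (beta blockers and certain calcium channel blockers) and 22 (glucose-lowering drugs other than insulin) are of the same kind.

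**The concern.** A 2x2 crossover uses each participant as their own control, so the participant should be in a comparable state in both periods. Followed as written, this plan establishes that by direct inquiry before one period only.

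Two things are at stake.

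- **Safety.** At both visits the participant eats a self-selected meal of 45 to 120 g carbohydrate without a meal bolus, with insulin delivery under an investigational algorithm. The exclusion criteria define who should not be exposed to this. A criterion that starts between visits would be missed unless someone happened to learn of it.
- **The comparison.** A course of corticosteroids, an infection or a new glucose-lowering drug in period 2 could alter the glucose response to the meal. The change falls inside the pair, so the random participant effect in Statistical methods does not remove it. The period term adjusts only for an average difference between periods, not for a disturbance in one person. The Power Analysis section gives the trial's purpose as feasibility and assessment of variability for a later study, so avoidable within-pair noise affects its main product.

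**Working it through.** The point is procedural, and the plan has no power or precision figure to reproduce: the sample size of 15 rests on feasibility. The first step is to trace every recheck that could reach period 2.

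| Check | Section | Reaches period 2? | Detects a new exclusion 9, 19, 21 or 22? |
|---|---|---|---|
| Medication, history and exclusion inquiry | 1 day Treatment Visits | No, tied to the first closed-loop study | Yes, if made |
| Pregnancy test if the last is over 7 days old | 1 day Treatment Visits | Yes | No |
| COVID-19 screening | Visit Procedures | Yes, for face-to-face visits | One infection only |
| Arrival glucose and ketone check | 1 day Treatment Visits, same paragraph as the inquiry | Not stated clearly | Not a new drug |
| Concomitant medication form | Recording of Data | No timing given | Only if completed and acted on before the visit |
| Investigator discretion | Withdrawal Criteria | Yes | Only if the change is already known |

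The mandatory list under Withdrawal Criteria names pregnancy, but not a newly met exclusion in general. Elsewhere the treatment-visit text says expressly when something applies to each visit or to all studies, so limiting the inquiry to the first study, matched by the form list, reads as a rule and not as loose wording.

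The interval can also exceed 30 days in practice. A participant stopped before lunch may return on another day for the second meal, and a terminated visit may be repeated (Discharge from clinic). Neither provision gives a time limit or asks for the inquiry again.

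**Illustration of size.** The documents give n = 15, a two-sided 0.05 level and a paired t-test. The frequency of new exclusions (p) and the shift they cause (k, in SDs of the paired difference) are assumptions.

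1. Chance that at least one of 15 participants is affected: 1 − (1 − p)^15. For p = 1%, 2%, 5% and 10% this is 14%, 26%, 54% and 79%.
2. Movement of the mean difference from one affected participant: k/15. For k = 1, 2 and 3 this is 0.07, 0.13 and 0.20 SD.
3. For scale, the 95% confidence interval half-width at n = 15 is 2.145/√15 = 0.55 SD. The largest of these movements is 0.20/0.55, or about 36% of the half-width.
4. Expected sample variance of the paired differences, in units of the undisturbed variance: 1 + [k²(1 − 1/15)]/14 = 1 + k²/15. For k = 1, 2 and 3 this is 1.07, 1.27 and 1.60.
5. Power, for a true effect of 0.78 SD (the effect giving 80% power at n = 15 by the noncentral t distribution): with one participant shifted against the effect by 1, 2 or 3 SD, simulation of 200,000 trials gives about 71%, 55% and 35%.

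Steps 2, 4 and 5 are conditional on one participant being affected. They show sensitivity, not an expected loss.

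**The case against.** The strongest opposing case is that other safeguards narrow the gap and that the statistical effect is modest. Much of this stands, and it limits what can be claimed.

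- **Eligibility as a whole.** A reader might infer that nothing about eligibility is checked again after the first visit. That is wrong: pregnancy is retested under the 7-day rule, COVID-19 screening applies, and the investigator may withdraw a participant at discretion. The gap is confined to the medication, history and exclusion inquiry.
- **Severe hypoglycemia or ketoacidosis between visits.** It is tempting to say that such a participant would enter period 2 in breach of exclusions 6 or 7. Those items look back from the screening visit, so a later event does not literally meet them. The Stopping Rules halt the entire study for such events, and Monitoring Procedures requires adverse events to be reported immediately. An event at home still has to become known, and the halt may be meant for events during closed-loop sessions, but the example does not carry the point.
- **Pump settings.** Stable settings are an inclusion criterion, and the inquiry as written does not cover them at either visit. This is not a difference between the first and second visits.
- **Bias towards one system.** Visit order is randomised, so changes arising before period 2 have no built-in direction by system. They add noise or chance imbalance. Even a 3 SD shift in one participant stays well inside the confidence interval half-width.
- **The arrival glucose and ketone check.** It may apply at both visits; the text is ambiguous. Even if it does, it cannot reveal a new drug.

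What does not stand is the suggestion that these safeguards close the gap. Each either covers a single condition or depends on someone already knowing what the omitted question would have revealed.

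**Conclusion.** The point holds in a limited form. The inquiry for newly developed exclusions is specified and recorded for the first closed-loop study only, while period 2 may begin up to 30 days later. Present-state exclusions 9 (apart from COVID-19), 19, 21 and 22 can therefore go unasked before the second exposure. That conclusion rests on the text alone.

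The consequences are a safety risk and added within-pair noise in a 15-participant crossover. The documents support neither a claim of systematic bias nor an estimate of how often this would happen. The figure of 0.13 to 0.20 SD on the mean difference assumes one affected participant and a shift of 2 to 3 SD. The change is still worth making, because the gap is a stated rule and closing it costs very little.

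**What to change.** 1. In 1 day Treatment Visits, state that the inquiry is made and recorded at the beginning of each closed-loop study, including any repeat visit or return for the second meal.
2. Under Recording of Data, add an assessment form for the second closed-loop study matching the one for the first.
3. In the same paragraph, state whether the arrival glucose and ketone check applies at both visits.
4. The protocol team should state what action follows when an exclusion is newly met, and reconcile it with the Withdrawal Criteria and the Stopping Rules. That is a clinical decision, and none is proposed here.
5. In Statistical methods, state how period-2 data are handled when an exclusion is found before or after the visit, and how period-1 data are used if period 2 does not take place.

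The cost is a few minutes of interview by staff already present and one more copy of an existing form. The downside is an occasional delayed or lost second visit. A lost visit would count towards the more than two non-completers that trigger multiple imputation under Missing data, so items 4 and 5 should be settled together.

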• To evaluate performance of the OHSU Robust R-AP closed-loop system versus the OHSU MPC closed-loop system in the 4 hours following the first meal period, as measured by other glycemic outcomes.

Study Hypothesis:

We propose that the use of the OHSU Robust R-AP closed-loop system as compared to the OHSU MPC closed-loop system will decrease AUC and increase the time in range as measured by sensed glucose values.

Endpoints

Primary Endpoint:

- Incremental AUC of postprandial glucose in the 4 hours following the start of first meal. AUC (mg/dL*min) will be calculated using a trapezoidal method [20], which sums all CGM values in the 4 hour period following the meal above the starting glucose.
- Percent of time with sensed glucose between 70 180 mg/dl in the 4 hours following the start of first meal.

Secondary Endpoints (all measured in the 4 hours following the start of meals):

- Percent of time with sensed glucose <70 mg/dl across the study duration
- Number of carbohydrate treatments (defined as 15 or 20 grams of carbohydrate)
- Number of provider-administered insulin injections due to hyperglycemia
- Mean sensed glucose
- Percent of time with sensed glucose <54 mg/dl
- Percent of time with sensed glucose >180 mg/dl
- Percent of time with sensed glucose >250 mg/dl
- Mean amount of insulin delivered per day (in units/kg)

Study Type

This is a single-center, crossover trial designed to compare the glucose control resulting from the use of the OHSU Robust R-AP system as compared to the OHSU MPC AP system.

Study Population

Study population will be adults with type 1 diabetes, ages 18-65 years of age. Younger participants are excluded as it is appropriate to assess safety first in the adult population. Fifteen participants will be recruited to participate in studies.

[figure not shown]
Power Analysis

This study is to obtain feasibility and assessment of variability in the primary outcomes that will inform a future larger, sufficiently powered efficacy study. A sample size of 15 is a feasible number to recruit and complete the study in timely fashion. This sample size will allow adequate estimation of the outcomes and variability of those estimates.

Protocol Summary:

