Participants will undergo two visits at OHSU that will evaluate missed meal bolus detection. Participants will arrive at approximately 7am for all visits, be monitored through the afternoon and discharged before dinner. See **Figure 1** for a diagram of the study flow. During each of these intervention visits, participants will wear an Omnipod to deliver insulin and a Dexcom G6 CGM to measure glucose. The closed loop system will receive activity data through a Polar M600 watch worn by the participant. The studies will test the ability of the system to adapt to a missed meal bolus. For one missed meal bolus study, glucose will be controlled using the Robust R-AP closed-loop mode. During the other missed meal bolus study, glucose will be controlled using the MPC closed-loop mode. For the R-AP study, participants will eat self selected meals at 10 am and 2pm. The 10am meal will be the only meal given during the MPC study. The 10am meal will be the same across both arms. A meal bolus will not be given before any meals.

Figure 1: Study Flow Design

Subject Criteria

Inclusion Criteria:

- 1. Diagnosis of type 1 diabetes mellitus for at least 1 year.
- 2. Male or female participants 18 to 65 years of age.
- 3. Current use of an insulin pump for at least 3 months with stable insulin pump settings for >2 weeks.

- 4. HbA1c $\leq 10.5\%$ at screening.
- 5. Total daily insulin requirement is less than 139 units/day.
- 6. Willingness to follow all study procedures, including attending all clinic visits.
- 7. Willingness to sign informed consent and HIPAA documents.

Exclusion Criteria:

- 1. Individual of childbearing potential who is pregnant or intending to become pregnant or breast-feeding, or is not using adequate contraceptive methods. Acceptable contraception includes birth control pill / patch / vaginal ring, Depo-Provera, Norplant, an IUD, the double barrier method (the woman uses a diaphragm and spermicide and the man uses a condom), or abstinence.
- 2. Any cardiovascular disease, defined as a clinically significant EKG abnormality at the time of screening or any history of: stroke, heart failure, myocardial infarction, angina pectoris, or coronary arterial bypass graft or angioplasty. Diagnosis of 2nd or 3rd degree heart block or any non-physiological arrhythmia judged by the investigator to be exclusionary.
- 3. Renal insufficiency (GFR < 60 ml/min, using the MDRD equation as reported by the OHSU laboratory).

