After a run-in period of 2 hours whereby the participants are using the AP algorithms, participants will eat self selected meals around 10 am. During the R-AP study only, another meal will be given four hours later around 2 pm. The self selected meals will have a minimum of 45 g of carbohydrates, and a maximum of 120 g of carbohydrates. These self selected breakfasts will be identical across both study sessions. Participants will not enter a meal bolus for the meals. CBG and blood ketone measurements will be taken every 30 min (for safety purposes only, not for input into the AP systems) until study discharge. If CBG >250mg/dL before the lunch meal, then study will be stopped early and the participant will be given the option to return on a different day for the second meal.

The study will be stopped if:

- (1) the CBG reaches > 300 mg/dL with ketones > 0.5 mM,
- (2) the CBG reaches > 300 mg/dL for over an hour (even when ketones are <0.5 mM),
- (3) the CBG reaches > 450 mg/dL,
- (4) participants exhibit nausea or vomiting or both.

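### A 250 mg/dL pre-lunch stop can act only at the R-AP visit, and the plan fixes neither its timing against the 4-hour primary window nor the scoring of a stopped visit

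*Combined protocol and SAP*

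**What the plan says.** Both primary endpoints cover the first meal. The Endpoints section defines the first as "Incremental AUC of postprandial glucose in the 4 hours following the start of first meal", summed by the trapezoidal method above the starting value. Percent time in 70-180 mg/dL uses the same 4 hours.

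The visits differ in meals. In the 1 day Treatment Visits section, "participants will eat self selected meals around 10 am", and then "During the R-AP study only, another meal will be given four hours later around 2 pm". The Protocol Summary confirms that "The 10am meal will be the only meal given during the MPC study".

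The same treatment-visit paragraph sets the monitoring: "CBG and blood ketone measurements will be taken every 30 min". It then adds: "If CBG >250mg/dL before the lunch meal, then study will be stopped early and the participant will be given the option to return". The stated purpose of that return is the second meal.

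A stopping list follows that is not limited to either visit. Its first item is "1) the CBG reaches > 300 mg/dL with ketones > 0.5 mM". The others are CBG above 300 mg/dL for more than an hour, CBG above 450 mg/dL, and nausea or vomiting.

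Two other places bear on the point. The missing-data paragraph under Statistical methods shortens a participant's observation time when that person leaves early. The Discharge from clinic section offers an optional repeat of any visit that ended prematurely.

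**The concern.** A stopping rule tied to lunch can operate only where there is a lunch, which is the R-AP visit. A CBG of 251-300 mg/dL meets this rule at R-AP and meets no item of the common list at MPC. The two systems could therefore be observed under different rules during the hours that define both primary endpoints.

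The sentence directly follows the 30-minute CBG schedule and names neither a single reading nor a clock time. Everything between the two meals is before lunch, and that stretch is the primary window.

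Incremental AUC is a sum over time and is not divided by the time observed. If an R-AP visit ends early and is scored on what was recorded, its AUC falls because the curve is shorter. The error favours R-AP, the direction of the study hypothesis.

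**Working it through.** The plan gives no figure for this point, so there is none to reproduce. The size depends on when the check falls.

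**Timeline.** The first meal is at about 10 am and lunch about 4 hours later, so the window is 4 × 60 = 240 min and closes at the planned lunch time. If CBGs run from the meal start (an assumption), they fall at +30, +60, ..., +240 min. The share of the window lost is (240 - stop time)/240:

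- stop at +90: 150/240 = 62.5%
- stop at +120: 120/240 = 50%
- stop at +210: 30/240 = 12.5%
- stop at +240: 0%

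**Missing-data rule.** The 3% limit is 0.03 × 240 = 7.2 min for a full window. If observation time is itself shortened at the stop, the lost minutes need not count as missing, and the CBG-based imputation need not be triggered.

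**One curve by hand.** Assume the same curve at both visits: linear from 150 to 290 mg/dL at 120 min, then linear to 240 at 240 min. It never reaches 300, so no glucose item of the common list stops it.

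- Full window: AUC = ½ × 120 × 140 + 120 × (140 + 90)/2 = 8,400 + 13,800 = 22,200 mg/dL·min. Glucose passes 180 at 120 × 30/140 = 25.7 min, so time in range is 25.7/240 = 10.7%.
- Any reading counts: CBG is 220 at +60 and 255 at +90, so R-AP stops at +90. AUC = ½ × 90 × 105 = 4,725, which is 21% of the full value. Time in range is 25.7/90 = 28.6%.
- Single check at +210: CBG is 290 - 50 × 90/120 = 252.5, so R-AP stops. AUC = 8,400 + 90 × (140 + 102.5)/2 = 19,312.5, which is 87% of full. Time in range is 25.7/210 = 12.2%.
- Single check at +240: CBG is 240. There is no stop and no loss.

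**Simulation with no true difference.** N = 15 and two-sided 0.05 come from the plan, as does the paired t-test. The rest is assumed:

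- curve b + r·(x·e^(1-x))², with x = time/peak time
- baseline b: mean 140, SD 20 mg/dL
- rise r: mean 80, 110 or 140 mg/dL, SD 30 between and 30 within participants
- peak time uniform on 90-150 min
- 3,000 trials per setting

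Only R-AP was cut at the 250 mg/dL check, and AUC was summed over the time observed. Entries are for mean rises of 80/110/140.

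| Reading | R-AP visits cut short | AUC bias | AUC false-positive rate | Time-in-range bias (points) | Time-in-range false-positive rate |
|---|---|---|---|---|---|
| Any CBG between meals | 26/50/74% | -29/-49/-67% | 0.47/0.94/1.00 | +4/+10/+16 | 0.07/0.28/0.76 |
| One check at +210 | 7/17/33% | -0.7/-2.4/-4.9% | 0.05/0.06/0.10 | +0.2/0.0/+0.5 | 0.05/0.04/0.03 |
| One check at +240 | 0% | +1.2/+0.1/+0.3% | 0.05/0.05/0.05 | -0.2/+0.1/0.0 | 0.05/0.04/0.03 |

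In the last row both visits are treated identically, so departures from zero reflect the simulation and not lost data. The common stops were not applied at either visit. They would shorten some MPC visits too, so the first row is likely overstated at the larger rises.

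**The case against.** The best defence is that the sentence is a gate on lunch. The participant comes back "on a different day for the second meal", which makes sense only if first-meal observation is complete. Lunch is planned for the end of the window, and discharge is only after 4 pm, so a stop at about 2 pm is early without touching the primary data. The treatment-visit text also describes what happens once glucose stops (1)-(3) are reached. If any reading above 250 mg/dL ended the visit, those three could hardly come into play at R-AP before lunch. I accept this as the more coherent reading.

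Three stronger inferences do not stand:

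- **R-AP alone gets extra attempts at the primary endpoint.** The return day is for the second meal, both endpoints use the first, and the repeat-visit provision covers either arm.
- **A 250 mg/dL stop moves the participant to investigator-calculated dosing.** That provision is tied to stops (1)-(3). What follows a 250 mg/dL stop is not stated.
- **The sentence contradicts the stopping list.** The list gives conditions that suffice for a stop and does not say that no other condition can. The two need reconciling because their joint operation is unclear.

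It is also fair to say that no passage prescribes comparing AUCs over unequal durations, and that multiple imputation is planned if more than two participants do not complete. But the plan does not say whether a visit stopped at lunch counts as incomplete, or whether CGM recorded after a stop is used. Even a gate reading leaves both meal times approximate, so a check made before lunch can fall short of +240 min.

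**Conclusion.** The concern holds as a one-arm stopping rule with undefined timing and undefined scoring. Two facts are certain from the text: the rule can act only at R-AP, and its threshold lies below every glucose level in the common list.

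A reader might infer that R-AP visits will be cut short inside the primary window and that the comparison is badly biased. The documents do not establish that. The wording permits it, but the gate reading fits the rest of the section better.

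The size follows the reading. AUC bias is about nil at +240 min, about -1% to -5% at +210 min, and -29% to -67% if any between-meal CBG counts. These figures rest on assumed curves, on observation ending at the stop, and on AUC being summed over the time left. They show direction and rough size and do not forecast this trial's results.

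This is a feasibility study of 15 participants with no power calculation, but it does plan two-sided 0.05 tests of R-AP against MPC. I would rate the point as one that should be fixed, below must-fix.

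**What to change.** 1. Reconcile the 250 mg/dL sentence with the stopping list beneath it and with the repeat-visit provision under Discharge from clinic. The threshold and the stopping rules remain the sponsor's decision.
2. If the check is meant as a gate on the second meal, say so, and time it from the actual start of the first meal so that it falls once the 4-hour window has closed.
3. Under Statistical methods, pre-specify one rule, identical for both visits, for how a visit stopped before +240 min enters AUC and time in range. Do not compare AUCs summed over unequal durations.
4. State that a return day for the second meal supplies no first-meal primary data.

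The cost is a short protocol clarification, a lunch that may be a few minutes later, and slightly more analysis work.
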